10.2.2 Secondary Efficacy Analyses

ORR and CR will be assessed as the proportion of subjects with an overall response based on the IWCLL NCI-WG criteria. The 95% confidence interval based on the Clopper-Pearson exact method for binomial distribution will be constructed for the calculated ORR and CR rates.

DOR, TTP, PFS, and OS will be analyzed by Kaplan-Meier methodology using data for all subjects defined in Section 5.1.1. Median time of each endpoint will be calculated and 95% confidence interval for median time of each endpoint will be presented.

Secondary quality of life endpoints will include all multi-item scales and single-item scales from the EORTC QLQ-C30, EORTC QLQ-CLL16, and EQ-5D-5L. Scores will be calculated based on the scoring manual for each instrument. The mean change score from baseline to post-baseline (Week 4, Week 12, Week 24, Week 36, Week 48, Week 60, Week 72, Week 84, Week 96, and Week 108/Final visit) will be summarized with the 95% confidence interval. Mean score with SD of baseline and each post-baseline visit also will be presented.

10.3 Subgroup Analyses of Quality of Life and Efficacy

To evaluate the impact of baseline conditions on quality of life subgroup analyses will be performed on the analysis population defined in Section 5.1.1. The following subgroups below will be used for quality of life analyses:

- 17p deletion status (deleted, not deleted)
- TP53 mutation (yes, no)
- Prior BCRi treated (yes, no)
- Prior number of oncology therapies (1, 2, ≥ 3)
- Baseline ALC ($< 25 \times 10^9/L$, $\geq 25 \times 10^9/L$; $< 100 \times 10^9/L$, $\geq 100 \times 10^9/L$)
- Baseline node size (< 5 cm, 5 cm to 10 cm, ≥ 10 cm)
- Hospitalized for TLS prophylaxis before venetoclax (yes, no)

The following subgroups below will be used for ORR and CR analyses on the analysis population defined in Section 5.1.1 and on previously untreated BCRi subjects, and on previously treated BCRi subjects:

- Sex (male, female)
- Race (White, Non-White)
- Age (< 65 , ≥ 65 ; < 75 , ≥ 75)
- ECOG status (0, 1, 2)
- 17p deletion status (deleted, not-deleted)
- TP53 mutation status (yes, no)
- Prior number of oncology therapies (1, 2, ≥ 3)
- Baseline ALC ($< 25 \times 10^9/L$, $\geq 25 \times 10^9/L$; $< 100 \times 10^9/L$, $\geq 100 \times 10^9/L$)
- Baseline node size (< 5 cm, 5 cm To 10 cm, ≥ 10 cm)

ORR and CR and their 95% CIs will be reported for each level of subgroups in a forest plot. KM plot for DOR and PFS will be also be provided for 17p deleted versus non-17p

del., TP53 mutation versus TP53 non-mutation, and prior BCRi treated versus prior BCRi naïve.

10.4 Handling of Multiplicity

There will be no multiplicity adjustments performed in this open arm study.

11.0 Safety Analysis

11.1 General Considerations

Safety data will be summarized for the safety population, and the population is defined in Subsection 5.1.1.

11.2 Analysis of Treatment-Emergent Adverse Events

All summaries/analyses involving AEs will include treatment-emergent adverse events (TEAE) only, unless otherwise specified. TEAE are defined as any event with onset after the first dose of venetoclax and no more than 30 days after the last dose of venetoclax. Events where the onset date is the same as the venetoclax start date are assumed to be treatment-emergent, unless the venetoclax start time and the AE start time are collected and the AE start time is prior to the venetoclax start time. If an incomplete onset date was collected for an AE, the AE will be assumed to be treatment-emergent unless there is evidence that confirms that the AE was not treatment-emergent (e.g., the AE end date was prior to the date of the first dose of venetoclax).

Treatment-emergent adverse events will be summarized by maximum severity grade level of each preferred term. Each adverse event will be assigned a grade level (grade 1, 2, 3, 4, or 5) by the investigator. If a subject has an AE with unknown severity, then the subject will be counted in the severity grade level category of "unknown," even if the subject has another occurrence of the same event with a severity present. The only exception is if the subject has another occurrence of the same AE with the highest grade level (grade 5). In this case, the subject will be counted under the "Grade 5" category.

Treatment-emergent adverse events will be summarized by relationship of each preferred term to venetoclax, as assessed by the investigator. If a subject has an adverse event with unknown relationship, then the subject will be counted in the relationship category of "unknown," even if the subject has another occurrence of the same event with a relationship present. The only exception is if the subject has another occurrence of the same adverse event with a relationship assessment of "Reasonable Possibility." In this case, the subject will be counted under the "Reasonable Possibility" category.

Adverse events will be coded using the Medical Dictionary for Regulatory Activities (MedDRA). The actual version of the MedDRA coding dictionary will be noted in the clinical study report.

The number and percentage of subjects with treatment-emergent adverse events will be tabulated by primary MedDRA System Organ Class (SOC) and preferred term (PT). The system organ classes will be presented in alphabetical order, and the preferred terms will be presented in alphabetical order within each system organ class.

Adverse Event

An overview of AEs will be presented consisting of the number and percentage of subjects experiencing at least one event for each of the following AE categories:

- Any treatment-emergent adverse event;
- Any treatment-emergent adverse event with reasonable possibility related to venetoclax by the investigator;
- Any treatment-emergent NCI toxicity (CTCAE V4.0) grade 3, or 4 adverse events;
- Any treatment-emergent NCI toxicity (CTCAE V4.0) grade 3, 4, or 5 adverse events;
- Adverse events broken down by NCI toxicity grade (Severity);
- Any treatment-emergent serious adverse event;
- Any treatment-emergent adverse event leading to discontinuation of venetoclax;

- Any treatment-emergent adverse event leading to venetoclax interruption;
- Any treatment-emergent adverse event leading to venetoclax dose reduction;
- Any treatment-emergent adverse event leading to death;
- Deaths.

The deaths in the overview summary include all deaths that occurring while the subject is still receiving venetoclax in this study and occurring off treatment within 30 days after the last dose of venetoclax.

For summary tables of AE by PT, subjects reporting more than one AE for a given PT will be counted only once for that term (most severe/highest grade incident for the severity tables and most related incident for the relationship tables). Subjects reporting more than one AE within an SOC will be counted only once for that SOC. Subjects reporting more than one AE will be counted only once in the overall total.

Adverse Events of Special Interest

Adverse events of special interest will be summarized. The list of adverse events of special interest is shown in [Table 3](#).

For each of the adverse event of interest, the number and percentage of subjects experiencing at least one treatment-emergent adverse event will be presented overall and by SOC and PT. In addition, a listing of treatment-emergent adverse events for subjects meeting each of the search criteria will be provided.

Table 3. Adverse Events of Special Interest

Risk	Search Criteria
Tumor Lysis Syndrome (three searches)	
 1) SMQ – "Tumour lysis syndrome" (Narrow-scope) 2) SMQ – "Tumour lysis syndrome" (Narrow) plus PT terms of "Hyperkalaemia," "Hyperuricaemia," "Hyperphosphataemia," "Hypocalaemia," "Blood potassium increased," "Blood uric acid increased," "Blood phosphorus increased," "Blood calcium decreased" 3) SMQ – "Tumour lysis syndrome" (Narrow) plus broad-scope terms with algorithm applied (ie., two events from category B and one event from category C required for a subject to be counted as having a TLS event)
Neutropenia	PT terms – "Neutropenia," "Neutrophil count decreased," "Febrile neutropenia," "Agranulocytosis," "Neutropenic infection," and "Neutropenic sepsis"
Serious Infection, Including Opportunistic Infections	SAEs in the SOC of "Infections and Infestations"
Second Primary Malignancy	SMQ – "Malignant tumours" (Narrow) and "Myelodysplastic syndromes" (Narrow)
Lymphopenia	PT terms – "Lymphopenia" and "Lymphocyte count decreased"
Anemia	PT terms – "Anaemia" and "Haemoglobin decreased"
Thrombocytopenia	PT terms – "Thrombocytopenia" and "Platelet count decreased"
Drug Induced Liver Injury (DILI)	SMQ – "Drug related hepatic disorders – comprehensive search"
Medication Error	SMQ – "Medication error" (broad)

SMQ = Standardised MedDRA Query;

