6.1.1 Definitions

6.1.1.1 Adverse Event

An adverse event (AE) is defined as any untoward medical occurrence in a subject or clinical investigation subject administered a pharmaceutical product and which does not necessarily have a causal relationship with this treatment. An adverse event can therefore be any unfavorable and unintended sign (including an abnormal laboratory finding), symptom, or disease temporally associated with the use of a medicinal (investigational) product, whether or not the event is considered causally related to the use of the product.

Such an event can result from use of the drug as stipulated in the protocol or labeling, as well as from accidental or intentional overdose, drug abuse, or drug withdrawal. Any worsening of a pre-existing condition or illness is considered an adverse event.

Worsening in severity of a reported adverse event should be reported as a new adverse event. Laboratory abnormalities and changes in vital signs are considered to be adverse events only if they result in discontinuation from the study, necessitate therapeutic medical intervention, meets protocol specific criteria (see Section 6.1.9 Toxicity Management) or if the investigator considers them to be adverse events.

For this protocol, disease progression is an efficacy endpoint. These data will be captured as efficacy assessment data only. Thus, events that are clearly consistent with the expected pattern of progression of the underlying disease (such as transformation to more aggressive histology) will result in discontinuation from the study and should not be recorded as adverse events but reported on the Study Completion eCRF. However, if a subject experiences an adverse event (e.g., pneumonia, pyrexia, fatigue, etc.) and is also found to have disease progression, report the adverse event. If there is any uncertainty as to whether an event is due to disease progression, it should be reported as an adverse event.

An elective surgery/procedure scheduled to occur during a study will not be considered an adverse event if the surgery/procedure is being performed for a pre-existing condition and the surgery/procedure has been pre-planned prior to study entry. However, if the

pre-existing condition deteriorates unexpectedly during the study (e.g., surgery performed earlier than planned), then the deterioration of the condition for which the elective surgery/procedure is being done, will be considered an adverse event.

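### In the severity-by-preferred-term tables, one ungraded record moves a subject with a known Grade 3 or 4 event to 'unknown', against the SAP's own highest-grade rule

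*SAP*

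**What the plan says.** Four statements in SAP section 11.2 bear on this.

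- The aim of the table: "Treatment-emergent adverse events will be summarized by maximum severity grade level of each preferred term".
- The rule for missing grades: a subject with an ungraded record goes to 'unknown' for that event, "even if the subject has another occurrence of the same event with a severity present". The single exemption is a subject who also has a Grade 5 occurrence.
- The rule for repeated events in tables by preferred term: the subject is counted once, at the "most severe/highest grade incident for the severity tables and most related incident for the relationship tables".
- The overview table, which is built differently: it gives the "number and percentage of subjects experiencing at least one event for each of the following AE categories", and one of those categories is "Any treatment-emergent NCI toxicity (CTCAE V4.0) grade 3, or 4 adverse events". A second row covers Grades 3 to 5.

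On how often a grade should be missing, the same section says: "Each adverse event will be assigned a grade level (grade 1, 2, 3, 4, or 5) by the investigator". On how several records of one event arise, protocol section 6.1.1.1 says: "Worsening in severity of a reported adverse event should be reported as a new adverse event".

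**The concern.** A table of maximum severity should show a subject with a documented Grade 4 event at Grade 4 or above. The missing-grade rule lets a single blank field override that. The highest-grade rule later in the section points the other way, since a record without a grade cannot be the highest-grade incident. Two programmers following different paragraphs would fill different cells for the same subject.

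Safety and tolerability will be evaluated under the stated objectives (protocol section 4.0, SAP section 4.1), and the severity table by preferred term is where a reader looks up how often a given toxicity reached Grade 3 or 4. An error there that runs in one direction only is worth removing even if it is small.

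**Working it through.** The documents give no figure that depends on this rule, so there is nothing to reproduce. The check applies both rules to the same records and then asks how large the difference could be.

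**Step 1: the two rules side by side.** Rule A is the missing-grade rule: Grade 5 if present, otherwise 'unknown' if any record is ungraded, otherwise the maximum. Rule B is the highest-grade rule: the highest known grade, or 'unknown' if no record is graded.

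| Records of one preferred term | Rule A | Rule B |
|---|---|---|
| 4 | 4 | 4 |
| 4, ungraded | unknown | 4 |
| 3, 1, ungraded | unknown | 3 |
| 1, ungraded | unknown | 1 |
| 5, ungraded | 5 | 5 |
| ungraded only | unknown | unknown |

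Wherever the rules differ, Rule A moves a subject from a known grade to 'unknown'. It never moves anyone into Grade 3 or 4. Relative to Rule B it can therefore only lower the Grade 3-4 rows.

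**Step 2: which outputs are touched.**

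- Severity tables by preferred term: affected.
- Overview rows for Grade 3-4 and Grade 3-5: these need only one qualifying event, so a known Grade 4 record is enough. Not affected on their face. The overview line that breaks events down by toxicity grade is less clearly protected.
- Special-interest tables (SAP section 11.2): counted overall and by system organ class and preferred term, not by grade. Not affected.
- Laboratory shift tables (SAP section 11.3.1): based on the maximum grade of laboratory values, with listings of Grade 3-4 values. Not affected.

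**Step 3: possible size.** Let m be the chance that a record is ungraded and k the number of other records of the same term for a subject who has a known Grade 3-4 record and no Grade 5 record. With independent records, the share moved to 'unknown' is 1 - (1 - m)^k. Both m and k are assumptions. Take 200 subjects (SAP section 4.3) and assume that 40 of them (20%) have a known Grade 3-4 record of the term. Each cell gives subjects moved, then the percentage shown in place of 20%.

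| m | k = 1 | k = 2 | k = 4 |
|---|---|---|---|
| 0.5% | 0.20; 19.90% | 0.40; 19.80% | 0.79; 19.60% |
| 1% | 0.40; 19.80% | 0.80; 19.60% | 1.58; 19.21% |
| 2% | 0.80; 19.60% | 1.58; 19.21% | 3.11; 18.45% |
| 5% | 2.00; 19.00% | 3.90; 18.05% | 7.42; 16.29% |

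As an example, for m = 5% and k = 4: 1 - 0.95^4 = 0.1855; 40 × 0.1855 = 7.42; 20% × (1 - 0.1855) = 16.29%.

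**The case against.** **The rule may be deliberate.** The missing-grade paragraph can be read as a specific exception to the general counting rule, giving one ranking: 5, then unknown, then 4, 3, 2, 1. The relationship summary has a similar rule, which suggests a house convention. There is a logic to it as well: when one record is ungraded, only Grade 5 is certain to be the maximum. This stands in part. A reader might infer that the two rules cannot both be programmed, and that goes too far. But the SAP never states the ranking, and stating it would still lose a known Grade 3 or 4. The relationship rule is not a full parallel either: it exempts the reasonable-possibility category, so the category that matters most for safety survives.

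**The remedy has its own error.** Under the highest-known-grade rule, a subject with Grade 1 plus an ungraded record appears at Grade 1, although the ungraded record might have been worse. This stands, and the fix has to disclose it.

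**Severe toxicity is reported elsewhere.** A reader might infer that the SAP understates severe toxicity as a whole. Step 2 shows that it does not. Grade 4 neutropenia would still count in the overview Grade 3-4 row, and low neutrophil values would still reach the laboratory shift tables. In the affected tables the subject is shown in a visible 'unknown' row and is not dropped.

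**Missing grades should be rare.** Protocol section 6.1.2 has the investigator rate every event, section 10.2 has case report forms reviewed for completeness, and section 11.0 adds logic and manual checks. This stands, and it favours the low end of the range.

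**Worsening events need not have more missing grades.** Because each worsening opens a new record, a reader might infer that the most severely affected subjects have the most chances of a blank. The documents do not support this. Section 6.1.2 requires the new record in order to reflect the change in severity, so it is a record whose grade someone has just considered.

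**Conclusion.** The point holds for the severity-by-preferred-term tables. The missing-grade rule conflicts with the highest-grade rule and with the stated aim of summarising maximum severity, and its effect on the Grade 3-4 counts goes one way only. That much follows from the text without assumptions.

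The size cannot be found from the documents. The range of about 0.2 to 7.4 of 40 subjects rests on an assumed 0.5% to 5% of ungraded records, 1 to 4 other records per subject, independence between records, and an assumed 20% of subjects with a known Grade 3-4 record of the term. Since every event is meant to be graded, the real effect is probably small. A claim of material bias is not supported. The reason to act is that the instructions conflict, the direction is certain, and the correction is nearly free.

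**What to change.** In SAP section 11.2:

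1. Replace the missing-grade rule with one that counts each subject at the highest known grade for the preferred term and uses 'unknown' only when no record of that term is graded.
2. Add a footnote to these tables giving the number of counted subjects who also have an ungraded record of the term.
3. State that the overview Grade 3-4 and Grade 3-5 rows use any known qualifying record, and say which rule the overview breakdown by grade follows.

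The cost is a few sentences and a small programming change. The downside is that a subject whose only known grade is 1 or 2, with another record ungraded, is shown at a grade that may not be the true maximum. The footnote discloses how many counted subjects have an ungraded record.

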6.1.4 Relationship to Study Drug

The investigator will use the following definitions to assess the relationship of the adverse event to the use of study drug:

Reasonable Possibility	After consideration of factors including timing of the event, biologic plausibility, clinical judgment, and potential alternative causes, there is sufficient evidence (information) to suggest a causal relationship.
No Reasonable Possibility	After consideration of factors including timing of the event, biologic plausibility, clinical judgment, and potential alternative causes, there is insufficient evidence (information) to suggest a causal relationship.

For causality assessments, events assessed as having a reasonable possibility of being related to the study drug will be considered "associated." Events assessed as having no reasonable possibility of being related to study drug will be considered "not associated." In addition, when the investigator has not reported causality or deemed it not assessable, AbbVie will consider the event associated.

If an investigator's opinion of no reasonable possibility of being related to study drug is given, an "Other Cause" of event must be provided by the investigator for the SAE.

[figure not shown]

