8.1.4.1 Adverse Events

Analyses of adverse events will include only "treatment-emergent" events, i.e., those that have an onset on or after the day of the first dose of study drug.

Analyses will not include those that have an onset greater than 30 days after the last dose of study drug.

Treatment-emergent adverse events will be summarized by preferred terms within a System and Organ Class according to the most current Medical Dictionary for Regulatory Activities (MedDRA). In addition, the percentage of subjects experiencing an adverse event at a NCI CTCAE toxicity grade, and relationship to study drug will be provided.

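### SAP 11.2 counts events with missing causality as 'unknown' where Protocol 6.1.4 treats them as associated, so related-AE counts can be lower than the protocol's rule gives, never higher

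*SAP*

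**What the plan says.** Protocol 6.1.4 (Relationship to Study Drug) gives the investigator two categories, 'Reasonable Possibility' and 'No Reasonable Possibility'. It says that "events assessed as having a reasonable possibility of being related to the study drug will be considered" associated, and then adds a default: "when the investigator has not reported causality or deemed it not assessable, AbbVie will consider the event associated". Protocol 8.1.4.1, in the statistics section, promises that "the percentage of subjects experiencing an adverse event at a NCI CTCAE toxicity grade, and relationship to study drug will be provided" but does not say how missing causality enters that summary.

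SAP 11.2 says that treatment-emergent events will be "summarized by relationship of each preferred term to venetoclax, as assessed by the investigator". For missing causality its rule is: "If a subject has an adverse event with unknown relationship, then the subject will be counted in the relationship category of" 'unknown', even where another occurrence of the event does have a relationship recorded. It allows one way out: "The only exception is if the subject has another occurrence of the same adverse event with a relationship assessment of" 'Reasonable Possibility', in which case the subject goes into that category.

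The adverse event overview in the same section has one row on causality: "Any treatment-emergent adverse event with reasonable possibility related to venetoclax by the investigator". It has no row for unknown relationship. For repeat events, the SAP takes the "most related incident for the relationship tables"; that sentence does not rank 'unknown', although the rule quoted above does.

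**The concern.** The protocol's scale has no 'unknown' category. An 'unknown' in the SAP tables is most naturally the not-reported or not-assessable case that Protocol 6.1.4 already settles in the conservative direction. The SAP neither cites that default nor explains why its tables do not use it.

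This matters because the study has one arm. With no control group, the causality assessment is the main planned means of separating drug-related events from background events, and safety and tolerability are a stated aim. As written, the sponsor could treat an event as associated under the protocol while the study's related-AE summary leaves the same event out. Any discrepancy runs in one direction, towards a more favourable related-AE rate. The SAP is conservative on a parallel gap in the same section: an event with an incomplete onset date is presumed treatment-emergent unless evidence shows otherwise.

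**Working it through.** The plan states no figure on this point, so there is nothing to reproduce. The check is to classify every possible set of causality records under both rules.

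**Inputs**
- Protocol 6.1.4: reasonable possibility = associated; not reported or not assessable = associated.
- SAP 11.2, relationship table: any 'Reasonable Possibility' record puts the subject there; otherwise any unknown record makes the subject 'unknown'; otherwise 'No Reasonable Possibility'.
- SAP 11.2, overview row: counted only if at least one event is 'Reasonable Possibility'.
- Planned number dosed: 200 (SAP 4.3, Protocol 8.2).
- Rate of missing causality: not in the documents. Assumed range: 0 to 5% of subjects.
- Assumption: the SAP's 'unknown' is the protocol's not reported or not assessable.

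**Step 1: one subject, one preferred term.** RP = Reasonable Possibility, NRP = No Reasonable Possibility.

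| Records for the term | SAP 11.2 | Protocol 6.1.4 | Lost from related count |
|---|---|---|---|
| RP | related | related | 0 |
| NRP | not related | not related | 0 |
| missing | unknown | related | 1 |
| RP + NRP | related | related | 0 |
| RP + missing | related | related | 0 |
| NRP + missing | unknown | related | 1 |
| RP + NRP + missing | related | related | 0 |

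Two of the seven patterns differ, both in the same direction.

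**Step 2: size of the gap for a term.**

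Related (protocol rule) − related (SAP) = number of subjects with at least one missing record and no RP record for that term.

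This is a count of subjects, so it is zero or positive.

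**Step 3: size of the gap in the overview row.** The formula is the same, with 'for that term' replaced by 'for any treatment-emergent event'. A subject with missing causality for one term and an RP rating for another is still counted here. A subject with missing causality and no RP rating on any event is not counted, and no other causality line in the overview shows that subject.

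**Step 4: scale.** One subject is 1/200 = 0.5 percentage points. With x the assumed share of subjects who fall in the gap for a given row:

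| x | Subjects (200 × x) | Shift in percentage points |
|---|---|---|
| 0% | 0 | 0 |
| 0.5% | 1 | 0.5 |
| 1% | 2 | 1.0 |
| 2% | 4 | 2.0 |
| 5% | 10 | 5.0 |

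The values of x are illustrations, not estimates. They apply to one row at a time, and the share for a single term need not equal the share for the overview row.

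**The case against.** The strongest reply is that the two documents describe different quantities. Protocol 6.1.4 sits in the adverse event section and says how the sponsor classifies an event. The SAP tables report the investigator's assessment and say so. A blank is not an investigator's judgement of reasonable possibility, and the protocol does not expressly extend its default to the tables. This stands in part. A reader might infer that the SAP reverses a statistical method of the protocol, and the documents do not support that: Protocol 8.1.4.1 is silent on missing causality, so the SAP fills a gap there. But 6.1.4 introduces its default for causality assessments in general, and names serious events only in its separate requirement for an alternative cause. Where the investigator gave no assessment, some default has to apply, and the protocol supplies one that the SAP does not mention.

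The SAP also has safeguards. Its exception rescues any subject with a 'Reasonable Possibility' record for the term, and 'unknown' outranks 'No Reasonable Possibility', so missing causality is never tabulated as unrelated. In the relationship table 'unknown' remains visible, so a reader can add it back. All of this stands for the relationship table; the overview row offers no such line.

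A further reply is that few gaps will remain. Protocol 6.1 has the investigator record relationship for each event, and Protocol 8.1.3 and 11.0 provide for data checks and quality control before extraction. These make blanks less likely, but they do not exclude an investigator's entry of not assessable.

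Finally, counting imputed events under a heading that credits the investigator would misdescribe them. That is right, and the fix has to deal with it.

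**Conclusion.** The two rules are not reconciled. The SAP's related-AE counts can be lower than Protocol 6.1.4 would give and can never be higher. The exposure is greatest in the overview row, where affected subjects are lost from view.

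A reader might go further and conclude that the related-AE rates will be understated. The documents do not support that. They give no rate of missing or not-assessable causality, and the difference is zero if there is none, or if every affected subject also has a 'Reasonable Possibility' record for the row in question. Each subject who does fall in the gap moves a percentage by 0.5 points, taking 200 dosed as planned.

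The conclusion rests on reading the SAP's 'unknown' as the protocol's not reported or not assessable. The tables of all treatment-emergent events, serious events, discontinuations, deaths and events of special interest do not depend on causality, and the primary endpoint is untouched. This is a worthwhile correction to the safety tables, not a threat to the study's main result.

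**What to change.** In SAP 11.2, replace the unknown-relationship rule with one sentence: treatment-emergent events with missing or not-assessable causality are counted as related, in line with Protocol 6.1.4, in both the relationship tables and the overview row.

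Label those rows as related including causality imputed under 6.1.4, so that they no longer read as the investigator's assessment alone. Add a footnote giving the number of subjects assigned in this way, which lets a reader recover the investigator-only count.

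If the sponsor prefers to keep tables on the investigator's assessment alone, the SAP should justify the departure, add an 'unknown' line to the overview, and give a supplementary count under the 6.1.4 rule.

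The cost is one sentence, a row label and a footnote, with no new data. The downside is that related-AE rates become slightly less favourable wherever causality is missing.
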